Dosing and randomization. After consent and baseline visits, eligible subjects will be randomized (allocation 1:1, blocks of 4 [AB and BA], randomization per BWH IDS) to receive the first period of study medication for 1 month (4 weeks). Allocations will be concealed from the subjects, investigators, physicians, and outcomes assessors. Patients will perform in random order the two study interventions:

- A) atomoxetine 80 mg plus oxybutynin 5 mg (full doses described)
- B) placebo

Half doses will be given on the first three nights (step-up dosing) per usual clinical use of atomoxetine. Placebos capsules will be given such that there are no differences in number or appearance of capsules taken between periods. There will be a 2-week washout between periods.

Duration. A 1-month duration is considered the minimum duration necessary for reliable assessment of short-term repeated-dose efficacy and effects on symptoms (e.g. Epworth Sleepiness scale assesses sleepiness over the last month) [20, 38-43]. Subjects will be treated for a 1-month period (30 days \pm 7 days).

If unexpected rescheduling of the on-treatment sleep study is necessary: First, we will seek to extend treatment for up to an additional 7 days (study drugs for 37 nights will be provided at the outset). Second, if rescheduling within this time frame is not possible, treatment will be paused and restarted as soon as possible with the goal of providing at least 7 days of treatment before the final sleep study. Third, the entire treatment period may be restarted if necessary. Having the subject attend a study visit after some duration of treatment will be prioritized over obtaining no sleep information for a given treatment period.

If a subject experiences difficulties on the full dose but not half dose (on or after treatment day 4): The participant may be advised to continue on the half dose for a longer duration, based on discussions with the (blinded) lead study physician. Having the subject adhere to the half dose will be prioritized over treatment non-use for a given treatment period.

PARTNERS HUMAN RESEARCH COMMITTEE DETAILED PROTOCOL

Version: April 11th, 2024

Sleepiness and Disease-Specific Quality of Life. Questionnaires after each study arm will assess:

- Epworth Sleepiness Scale (ESS).
- Functional Outcomes of Sleep Questionnaire (FOSQ) and Sleep Apnea Quality of Life Index (SAQLI) to assess disease-specific quality of life.

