Statistical analysis plan. We will perform intention-to-treat analysis, with values imputed for any study arm that was started but not complete (any dose taken) per multiple imputation with chained equations (see below). The quantitative primary outcome variable will be the percent change in apnea-hypopnea index (AHI) from baseline; the difference in this outcome variable between intervention and placebo will be evaluated (mixed model analysis, see below). Percent change from baseline will be used rather than absolute change because (1) statistical power in the single-night study was considerably greater when using the percent change versus absolute change, (2) the absolute but not percent change was strongly correlated with the baseline AHI, suggesting that the change in AHI with treatment is proportional to the baseline AHI, and (3) percent change is easy to interpret clinically. Standard linear mixed-effects model analysis for crossover studies [50-53] will evaluate the effect of intervention versus placebo on the outcome (fixed effect), independent of randomization sequence (AB or BA, i.e. carryover effects) and period (i.e. effect of time) as fixed effects, with each patient treated as a random effect; the approach also enables incorporation of incomplete data. We will also report the *response rate* i.e. percentage of patients who had a 50% percent reduction in AHI. Secondary outcomes will also be expressed as changes from baseline (percent change in arousal index; absolute change in nadir oxygen saturation, Epworth Sleepiness Scale, Functional Outcomes of Sleep Questionnaire) and assessed using the same approach. Per-protocol analysis will also be assessed to examine on-treatment effects (adherence \geq 80%). Variables will be transformed if necessary to provide a normal distribution before analysis (typically $x_{\text{transformed}} = x/(2-x)$) for AHI; 95% CI will be presented based on back-transformed results. P<0.05 will indicate statistical significance.

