Statistical analysis plan—Physiological determinants. Tests are designed to illustrate that each trait *explains* individual differences in the *response to therapy* (defined below). We will prospectively-test the hypothesis that greater pharyngeal collapsibility determines a reduced response to therapy (linear regression, *response to therapy* versus Vpassive). We will also separately test the hypotheses that a reduced muscle responsiveness, reduced baseline muscle activation, a higher arousal threshold, and a lower loop gain will facilitate a greater response to therapy (linear regression). The primary outcome variable (*response to therapy*) will be calculated by assessing the percent reduction in AHI from baseline with intervention (at 1 month) minus the percent reduction in AHI from baseline with placebo, i.e. consistent with Aim 1. Per-protocol analysis will be used because the study aims to explain inter-individual physiological responses. All questions are of separate scientific relevance and will not be adjusted for multiple comparisons. Multivariable regression will confirm whether baseline physiological variables remain predictive after adjusting for baseline apnea-hypopnea index.

Commonly, knowledge of multiple traits *in combination* best predicts outcomes. We will therefore perform a multivariable linear regression analysis (with interactions and squared terms, as needed, to capture non-linear relationships when evident) to describe how the traits combine to determine responses to therapy. This approach has been used successfully previously [46] and has strong physiological rationale (i.e. in those with milder collapsibility, higher loop gain leads to therapeutic failure).

Statistical analysis plan—Clinical predictors. We will build a multivariable model to *predict* individual differences in the response to therapy (defined above) using 1) routine baseline polysomnographic variables (including ratio of apneas to total events), and 2) estimated polysomnographic phenotypic traits (described above). In both cases, as performed previously

PARTNERS HUMAN RESEARCH COMMITTEE DETAILED PROTOCOL

Version: April 11th, 2024

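### Aim 2's individual response carries any period effect with opposite sign in the two sequences, and no Aim 2 model adjusts for it; adding sequence would protect precision at almost no cost

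*Combined protocol and SAP*

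**What the plan says.** The Aim 1 statistical analysis plan (section VI) estimates the treatment effect from a linear mixed model, "independent of randomization sequence (AB or BA, i.e. carryover effects) and period (i.e. effect of time) as fixed effects".

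The Aim 2 plan for physiological determinants reduces the two treatment periods to one number per patient: percent AHI reduction on AtoOxy "minus the percent reduction in AHI from baseline with placebo, i.e. consistent with Aim 1". The leading test is a "linear regression, *response to therapy* versus Vpassive", and the other traits are tested separately in the same way. The one adjustment named for these tests is baseline severity: "Multivariable regression will confirm whether baseline physiological variables remain predictive after adjusting for baseline apnea-hypopnea index". The analysis set is restricted: "Per-protocol analysis will be used because the study aims to explain inter-individual physiological responses". The multi-trait regression and the clinical-predictor models use the same response. None of them names period or sequence. The imputation paragraph uses both, but only to fill in missing outcomes.

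On design, section V (Dosing and randomization) gives "allocation 1:1, blocks of 4 [AB and BA], randomization per BWH IDS" and "There will be a 2-week washout between periods".

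**The concern.** A within-patient difference removes stable patient characteristics but not a period effect. AB patients take AtoOxy in period 1 and BA patients take it in period 2, so a general drift between periods lowers the difference in one group and raises it in the other. No baseline trait can explain that component, so it sits in the residual of every Aim 2 regression. Sequence is known for every patient and would account for it.

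The background section introduces the Aim 2 question, which patients benefit, as the most important one. The physiological tests are planned on 36 patients at 88% power, which leaves 8 points above 80%. In the clinical-predictor models the same shift enters every held-out response, which lowers apparent cross-validated performance and adds noise to backward elimination.

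**Working it through.** **Inputs from the documents**
- N=36, R-squared 0.25, alpha 0.05, stated power 88% (Aim 2 Power analysis). Two-sided testing is assumed.
- SD of percent change in AHI: 19 points, from the preliminary study (Aim 1 Power analysis). It is read here as the SD of the within-patient difference, because a paired t-test with N=48 on that reading reproduces the neighbouring powers: Epworth 80.7% (stated 80%), nadir saturation 98.9%, arousal index 89.8%, FOSQ 99.2%.
- 1:1 allocation to AB and BA.

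**Assumed.** The period effect d. The plan mentions "period (i.e. effect of time) as fixed effects" in Aim 1 but gives no size, so a range of 0 to 15 points is shown.

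**Step 1: the plan's own figure.** With the Fisher z approximation, power = Phi(atanh(sqrt(R²)) × sqrt(N-3) - 1.96). Here atanh(0.5) × sqrt(33) = 0.549 × 5.745 = 3.156, and Phi(3.156 - 1.96) = Phi(1.196) = 88.4%. The stated 88% is reproduced, and the calculation has no period term.

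**Step 2: how d enters.** Let tau_i be patient i's response free of period effects.
- AB patients: response = tau_i - d
- BA patients: response = tau_i + d

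The sequence means differ by 2d. With equal groups the variance rises by d², so without a sequence term R² becomes 0.25 / (1 + d²/SD²). At SD 19 (SD² = 361):
- d=5: 0.25 / (1 + 25/361) = 0.234
- d=10: 0.25 / (1 + 100/361) = 0.196
- d=15: 0.25 / (1 + 225/361) = 0.154

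With a sequence term d drops out, and the price is one degree of freedom (N-4 replaces N-3 in the formula).

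**Step 3: power at N=36, SD 19, R-squared 0.25 net of period.** Simulation used 40,000 trials per setting.

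| d (points) | Fisher z, without | Fisher z, with | Simulated, without | Simulated, with |
|---|---|---|---|---|
| 0 | 88.4% | 87.4% | 89% | 88% |
| 5 | 85.8% | 87.4% | 87% | 88% |
| 10 | 77.9% | 87.4% | 79% | 88% |
| 15 | 66.4% | 87.4% | 67% | 88% |

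Break-even is near d=3 (Fisher z 87.5% without, 87.4% with). A 22/14 split between sequences gives the same pattern at d=10.

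**Step 4: sensitivity to the SD.** At SD 30, d=10 gives 84.2% without sequence by Fisher z (about 85% simulated) against 87.4% (about 88%) with it. At d=5 the two are equal, at about 87.4%.

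**Step 5: sensitivity to the meaning of R-squared.** Suppose 0.25 already includes period noise. The planned test then keeps 88%. Net of period, R² is 0.25 × 361/(361 - d²): 0.269 at d=5 and 0.346 at d=10. With sequence added, power is about 90% and 97%.

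**Step 6: type I error.** With no true association, simulated rejection was 4.6% to 5.2% with or without sequence, for d from 0 to 19.

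**Step 7: N=48, R-squared 0.20 (clinical predictors).** The stated 81% is not reproduced: Fisher z gives 89.8% with no period effect, so the plan's figure is conservative. Without sequence, power is 87.4% at d=5, 80.2% at d=10 and 69.1% at d=15; with sequence it is 89.1%.

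**The case against.** The best counter-argument is that nothing need be lost. The plan defines R-squared 0.25 as the association with the response as constructed, so period noise may already be counted and the 88% stands. This reading is legitimate. Under it the sequence term is a gain over plan rather than a recovery of lost power.

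The size is also open. A loss of about 10 points needs d=10, roughly half an SD of systematic drift, in a trial with a two-week washout, instructed consistency of supine time across clinical studies, and a blinded scorer. At d=5 the loss is about 2 points. The SD of 19 comes from a preliminary study that was mainly a single-night comparison; a larger SD at one month would shrink the loss. At N=48 the plan's stated 81% is roughly met even at d=10. All of this stands, and it makes the magnitude conditional.

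Three stronger inferences are tempting and are not supported:
- **That the plan contradicts itself.** The phrase about consistency with Aim 1 can be read as describing the outcome measure (percent change, intervention against placebo), not the model.
- **That the Aim 2 subset is unbalanced by sequence.** No document says so. Randomization follows the baseline visits, so declining the physiology night should not depend on sequence. Per-protocol losses could upset the balance; it is not guaranteed, but imbalance is not shown.
- **That Aim 2's findings would be biased or falsely positive.** Sequence is randomized, and type I error holds.

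None of this removes the omission: no section brings period or sequence into an Aim 2 model.

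**Conclusion.** The point holds as a matter of precision. Any period effect enters the Aim 2 response with opposite sign in the two sequences, and the planned regressions leave it in the residual although Aim 1 adjusts for it. A reader might infer that the Aim 2 tests are underpowered as planned. The documents do not establish that, because they give no period effect and do not say whether R-squared 0.25 is net of it.

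On the assumptions of SD 19 and R-squared net of period, the term gains nothing below about d=3, about 2 points at d=5, about 10 at d=10 and about 20 at d=15. The gain at d=10 falls to about 3 points at SD 30. The case for acting rests on asymmetry: at most about 1 point of power is given up if there is no period effect, against a useful gain if there is a moderate one.

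**What to change.** In the Aim 2 plan for physiological determinants, state that randomization sequence (AB/BA) is a forced covariate in every regression: single-trait, adjusted for baseline AHI, and multi-trait.

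If a mixed model is preferred, it must contain treatment, period, sequence, the trait main effect and the treatment-by-trait interaction. Leaving out the main effect is not harmless. In small simulations (150 runs each) with a trait that acted equally under both treatments and no true interaction, the interaction was significant in 21% to 30% of runs, against about 5% to 7% with the main effect included.

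In the clinical-predictor models sequence should be a nuisance term only, since it cannot predict response in a future patient. In each leave-one-out loop, estimate the period effect from the training patients, remove it from their responses before selection, and apply the same correction to the held-out patient's response.

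The cost is one degree of freedom, about 1 point of power if there is no period effect, plus a sentence for the regressions and a short specification of the cross-validation step. No new data, visits or patients are needed. The change should be made before unblinding.

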- Conditions likely to affect obstructive sleep apnea physiology: neuromuscular disease or other major neurological disorder, heart failure (also below), or any other unstable major medical condition.
- Respiratory disorders other than sleep disordered breathing: chronic hypoventilation/hypoxemia (awake $\text{SaO}_2 < 92\%$ by oximetry) due to chronic obstructive pulmonary disease or other respiratory conditions.
- Other sleep disorders: periodic limb movements (periodic limb movement arousal index $> 10/\text{hr}$), narcolepsy, or parasomnias.
- Contraindications for atomoxetine and oxybutynin, including:
 - hypersensitivity to atomoxetine or oxybutynin (angioedema or urticaria)
 - pheochromocytoma
 - use of monoamine oxidase inhibitors
 - diagnosed benign prostatic hypertrophy, urinary retention
 - suspected benign prostatic hypertrophy / urinary retention based on a positive answer to either of the following questions:
 - “During the last month, when urinating, have you had the sensation of not emptying your bladder completely more often than 1 out of 5 times?”
 - “During the last month, have you had a weak urinary stream more often than 1 out of 5 times?”
 - untreated narrow angle glaucoma
 - bipolar disorder, mania, psychosis
 - history of major depressive disorder (age < 24).
 - history of attempted suicide or suicidal ideation within one year prior to screening
 - clinically significant constipation, gastric retention
 - pre-existing seizure disorders
 - clinically-significant kidney disorders ($\text{eGFR} < 60 \text{ ml/min/1.73m}^2$)
 - clinically-significant liver disorders
 - clinically-significant cardiovascular conditions
 - severe hypertension ($\text{SBP} > 180 \text{ mmHg}$ or $\text{DBP} > 110 \text{ mmHg}$ measured at baseline*)
 - cardiomyopathy ($\text{LVEF} < 50\%$) or heart failure
 - advanced atherosclerosis
 - history of cerebrovascular events
 - history of cardiac arrhythmias e.g., atrial fibrillation, QT prolongation
 - other serious cardiac conditions that would raise the consequences of an increase in blood pressure or heart rate
 - myasthenia gravis
 - pregnancy/breast-feeding
- Allergy to lidocaine (Aim 2 only)
- Claustrophobia
- Pregnancy or nursing

PARTNERS HUMAN RESEARCH COMMITTEE DETAILED PROTOCOL

Version: April 11th, 2024

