On arrival, the study will be explained in detail and an assessment will be made by an investigator to ensure the study procedures can be performed and written consent will be obtained by a licensed physician investigator. If the subject enrolled is a premenopausal woman, we will perform a urine pregnancy test at this visit.

COVID-19 Alternative: Consent Video Call

If participants are unable to attend an in-person visit (i.e. to minimize risk of highly infectious diseases like COVID-19), participants will take part in a video call with the consenting doctor to obtain consent (Zoom). All procedures described above will take part during this video call. The subject will already have received a copy of the consent form and will sign and mail it back to the consenting doctor who will then sign it. A copy of the signed consent form will be sent back to the subject. If the subject is a premenopausal woman, a pregnancy test will also be sent prior to the video call, and we will ask her to perform the test and we will verify the results. All questionnaires will be sent to the subject to be completed in their home.

2. Baseline Clinical Sleep Study

A baseline clinical sleep study (see ***Measurements and Equipment—Clinical***) will also be performed to assess eligibility. The baseline study will be used to determine if the subject has an apnea-hypopnea Index (AHI) greater than 15 events per hour. If their AHI is found to be less than

PARTNERS HUMAN RESEARCH COMMITTEE DETAILED PROTOCOL

Version: April 11th, 2024

15 on the baseline visit, they will not be randomized and participation will be discontinued. If a subject has completed a Baseline Clinical Sleep Study with the same measurements and equipment used for this study within 3 months of enrollment, we will use the previous study and they will not be asked to do this repeat Baseline Clinical Sleep Study.

Subjects will also complete baseline questionnaires (see below).

3. Baseline Physiological Sleep Study

A baseline physiological sleep study (see ***Measurements and Equipment— Physiological***) will also be performed to assess the mechanisms causing sleep apnea. We may allow subjects who decline the physiological study (Aim 2) to take part in Aim 1.

3. AtoOxy Treatment

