- Visual Analog Scales (VAASQ) and Treatment Satisfaction (VASTS, treatment only)
- Enthusiasm for continued therapy (ECT, treatment only; i.e. subjects will answer whether they would choose to continue using the treatment if given the opportunity)

Adherence. Nightly adherence will be monitored using electronic pill containers (MEMS cap) with real-time wireless monitoring capabilities that will keep the study staff informed of adherence throughout the study; direct feedback from technology (text message), and indirect feedback from study staff will serve to maximize adherence. We will also assess adherence through patient self-report and pill counts.

Sleep study. After 1 month of treatment at home, the subject will attend an overnight sleep study at the hospital (BWH, Tower 9A) and will perform a sleep study after taking the last dose of study medication for the treatment period (see **Measurements and Equipment—Clinical**). On these treatment studies, once all the equipment has been secured, subjects will be given their medication to take (30 min before lights out).

Safety Monitoring. See Data and Safety Monitoring Plan for details. In brief:

- Incident adverse events (AE) and any serious adverse events will be monitored throughout the study period and for 2 weeks after the last dose. Patients will be contacted by telephone (days 1, 3, 7, 14, 21, 28 of intervention; 7, 14 days after completion) and in person at the 1-month visit (day 30), following a standardized framework, to ensure timely reporting and clinical assistance if required. Patients will be asked to describe the incidence and severity of common side effects by checklist and any other adverse events.
- At each study visit we will also measure
 - effects on sleep parameters (including total sleep time, proportion of REM sleep, proportion of slow wave sleep, proportion of stage 1 sleep, arousal frequency)
 - effects on sleepiness and quality of life (ESS, SAQLI, VASSQ, and FOSQ)
 - overnight heart rate and evening/morning supine blood pressure (triplicate),
 - Brief Psychiatric Rating Scale (BPRS) to monitor for the potential emergence of suicidal ideation or behavior
 - medication tolerance based on adherence

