The morning after the sleep study, supine blood pressure will be measured (triplicate), equipment will be removed, side effects will be assessed systematically from a list of the possible side effects of all drugs used in the trial. Five Visual Analog Scales will be performed (Sleep Quality, Excessive Fatigue, Waking Unrefreshed, Low Energy, and Treatment Satisfaction), and subjects will also be asked if they would continue taking the medication if given the opportunity.

Measurements and Equipment—Physiological

In addition to the clinical studies, subjects will undertake the following:

- An esophageal catheter will be inserted after one nostril is anesthetized with 4% lidocaine (~1 ml of used). The tip of the pressure catheter will be located in the stomach. Once in place, the catheter will be taped at the nose to ensure it does not move. The integrity of the signal will be checked through a maneuver whereby inspiratory force is generated against a temporarily-occluded airway.
- For the majority of the night, patients will breathe spontaneously. For approximately 1-2 hours towards the start of the night, a modified CPAP device (Pcrit 3000, Philips Respironics, Murrysville PA) will be used to measure (A) eupneic ventilation, by using a

**PARTNERS HUMAN RESEARCH COMMITTEE
DETAILED PROTOCOL**

Version: April 11th, 2024

therapeutic level that keeps the airway open, and (B) the passive and active collapsibility by lowering and raising CPAP to manipulate ventilation and ventilatory drive. The CPAP device has been modified to enable delivery of both positive and negative continuous airway pressure. When used, the device will be attached to the mask.

- Subjects will be asked to remain in the supine position for as long as possible during the night.

If any data collected are considered insufficient, the subject may be asked to repeat the whole study or a part of it.

COVID-19 Alternative: Home Sleep Testing (for all nights EXCEPT the physiology night)

If participants are unable to attend an in-lab sleep study (i.e. to minimize risk of highly infectious diseases like COVID-19), subjects will perform home sleep tests. If the subject is a premenopausal woman, a pregnancy test will be sent prior to the home sleep tests. We will ask her to perform the test and we will verify the results in a Zoom video call.

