rate will be monitored continuously in all studies. Blood pressure monitoring will be performed on arrival, before sleep, and after sleep at all study visits.

- iv. Resuscitation equipment is readily available should the need arise. CPAP and 100% oxygen are available in the study rooms and can be quickly provided to the patient if needed. However, this seems unlikely.
- v. While the clinical sleep studies in the laboratory are noninvasive, the physiological studies (with esophageal catheterization) are somewhat invasive and there is a risk that subjects may be sleepier than usual in the morning. Thus, subjects will have the opportunity to sleep without instrumentation for as long as they would like before driving home. We will also offer a cab voucher to those who did not drive.
- vi. Women will have a urinary human chorionic gonadotropin test at each study visit to confirm absence of pregnancy.
- vii. In the case of adverse effects, each subject will be given the responsible study clinician's ([name]) cell phone number, and the principal investigator's cell phone number to contact at any time (24/7) regarding questions or complications; subjects will be strongly encouraged to call the study team. [name] will facilitate referrals for further medical care when appropriate.
- viii. During each period of the study, subjects will be contacted (e.g. telephone) for systematic safety assessment (adverse event checklist) according to a regular schedule (see above), including during the washout period after study completion. Subjects will additionally be asked to contact study staff if adverse events occur.
- ix. When used clinically, the study medications are not tapered-down before discontinuation (stopping). We also emphasize that there is data demonstrating no significant rebound/withdrawal effects of atomoxetine (in contrast to other noradrenergic agents/antidepressants) [62]. Nonetheless, subjects will be asked to contact the lead study clinician to discuss any concerning rebound/withdrawal effects after stopping study medications, and will receive advice on appropriate actions to mitigate symptoms, including delaying further study periods or discontinuation (see criteria below) when appropriate.

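### On the in-lab pathway no pregnancy test is described between the end of period 1 and the first period 2 dose, and the next test falls on the last-dose night

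*Combined protocol and SAP*

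**What the plan says.** Section III names pregnancy twice: once in the list of contraindications to the two drugs, and again as a separate exclusion, "Pregnancy or nursing".

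Testing is described in three places:
- Section V, Screening and Consent visit: "If the subject enrolled is a premenopausal woman, we will perform a urine pregnancy test at this visit". The remote version uses a mailed test with the result verified on a video call.
- Section IX, Protection Against Risks, item vi: "Women will have a urinary human chorionic gonadotropin test at each study visit to confirm absence of pregnancy".
- Section V, COVID-19 Alternative: Home Sleep Testing: "If the subject is a premenopausal woman, a pregnancy test will be sent prior to the home sleep tests". The result is again verified by video call.

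The contact schedule is in section V, AtoOxy Treatment. Safety Monitoring states: "Patients will be contacted by telephone (days 1, 3, 7, 14, 21, 28 of intervention; 7, 14 days after completion"), then "and in person at the 1-month visit (day 30"). The Sleep study paragraph places that visit at the end of the month at home, where the participant "will perform a sleep study after taking the last dose of study medication for the treatment period". Between the two periods, "There will be a 2-week washout between periods".

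Item i of Protection Against Risks adds that a physician checks the exclusion criteria by history and examination before drug is given. It names no pregnancy test and does not say that the check is repeated before period 2.

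**The concern.** A test tied to visits protects against exposure only if a visit comes shortly before dosing. In this crossover the visits described before period 1 are consent and the baseline nights. After that, each period has one visit, at its end. Nothing described opens period 2, so a pregnancy that began late in period 1 or during the washout would not be picked up by a scheduled test until period 2 dosing was essentially over. In the placebo-first sequence, that is the participant's first exposure to the active drugs.

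The matter is not remote from the protocol's own thinking. Enrollment starts at age 21, item xi of Protection Against Risks foresees that a participant may learn of a pregnancy during the study, and the definition of a serious adverse event includes birth defects. The purpose that item vi gives for the test is not met at the start of period 2 if the schedule is followed as written.

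**Working it through.** The plan gives no figure to reproduce. The check is a timeline built from the plan's own intervals.

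**Inputs**
- Washout: 14 days (section V, Dosing and randomization).
- Treatment duration: 30 ± 7 days, so 23 to 37 (section V, Duration). The Dosing paragraph also describes the month as 4 weeks, or 28 days.
- In-person contact within a period: one, at day 30, the last-dose night (Safety Monitoring; Sleep study).
- Dose timing at that visit: after the sensors are fitted, 30 minutes before lights out (Sleep study).
- Expected number randomized: 60 (section VI, Power analysis, Aim 1).
- Expected men:women ratio: 2:1 (section III).
- Allocation: 1:1 to AB or BA, where A is AtoOxy and B is placebo (Dosing and randomization).

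**Step 1. Last described test to first period 2 dose.** The last test is at the visit ending period 1, so the interval equals the washout: about 14 days. It is longer if period 2 is delayed, which Protection Against Risks item ix allows.

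**Step 2. Interval between the two on-treatment tests.** Interval = washout + period 2 duration.
- 23 days: 14 + 23 = 37 days
- 28 days: 14 + 28 = 42 days
- 30 days: 14 + 30 = 44 days
- 37 days: 14 + 37 = 51 days

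Pausing or restarting treatment, which the Duration paragraph permits, would lengthen this further.

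**Step 3. Doses taken before the period 2 test.** The last dose is given at the visit itself. If the test is done on arrival, the doses already taken are duration − 1: 29 of 30 (22 of 23 to 36 of 37 over the window). If the test follows the dose, all have been taken. The protocol does not state the order.

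**Step 4. Number concerned.** Women randomized: 60 × 1/3 = 20. Women in sequence BA, whose period 2 is AtoOxy: 20 × 1/2 = 10. Only some are premenopausal, and the protocol gives no number. Women in sequence AB take placebo in period 2.

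**Step 5. The same check for period 1 and for the home pathway.**
- Period 1: the consent-visit test comes before any dosing, and the baseline nights add tests when they take place. A baseline study from the previous 3 months can be reused and the physiology night can be declined, so the consent test may be the only one. No maximum interval from consent to first dose is given.
- Home pathway: the kit is sent ahead of the home sleep tests, and the sleep device is mailed together with the medication. No test day is fixed, so the test could fall before the first dose or near the sleep study.

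**The case against.** The best case for the plan has four parts.

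1. **A physician check already exists.** Item i of Protection Against Risks promises that exclusion criteria are ruled out before drug is given. This bears on the point and belongs among the passages to reconcile. It does not close the gap, because it names no test and is not stated for each period.

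2. **Participants are in regular contact.** Six telephone contacts per period and round-the-clock access to the clinician (item vii) give a participant ways to report a pregnancy. That stands, but it depends on her already knowing or suspecting it; the test is meant not to depend on that.

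3. **The documents may be incomplete.** There is no schedule-of-assessments table, in-lab dispensing is not described, item viii gives the telephone only as an example of contact, and the Data and Safety Monitoring Plan is not supplied. A check at the start of period 2 may exist elsewhere. This stands as a limit: the point concerns what the protocol describes.

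4. **Retest frequency is a design choice.** The entry criteria and the repeat testing do not contradict each other in the strict sense. That is fair, but the timing still fails item vi's own purpose for period 2.

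A reader might go further and infer that dosing in both periods starts untested, that the test always comes after the whole exposure, or that the home pathway has the same delay. The documents do not support these readings. Period 1 is preceded by at least the consent test, the last dose may follow the period 2 test, and home timing is undefined rather than shown to be late. Nor can the absence of a contraception requirement be held against the plan, since consent pages were removed from the text.

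**Conclusion.** The point holds for period 2 on the in-lab pathway. As described, the last pregnancy test is about 14 days or more before the first period 2 dose. The next is about 44 days after that test (37 to 51), when all but possibly the last dose have been taken. This coincides with first AtoOxy exposure for about 10 of the roughly 20 women expected, of whom an unstated number are premenopausal.

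These figures assume that the described visits are the only ones, that the washout runs its planned 14 days, and that the 2:1 ratio and 1:1 allocation hold among 60 randomized. For period 1 the issue is only the unspecified interval from the consent test to the first dose. For the home pathway it is only the undefined test day. It is a gap in enforcing a stated exclusion, limited in numbers but bearing on safety and cheap to settle.

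**What to change.** Reconcile the following so that the protocol states how pregnancy status is established relative to the start of dosing in each period, including period 2:
- section III, where pregnancy is a contraindication and an exclusion;
- section V, Screening and Consent visit, including the interval from that test to the first dose;
- section V, AtoOxy Treatment, on the contact schedule and the last-dose visit, including the order of test and dose;
- section V, Home Sleep Testing, on the day of the test relative to dosing;
- section IX, Protection Against Risks, items i and vi.

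The same edit should settle who is tested: item vi refers to women without qualification, whereas the consent and home-testing text refers to premenopausal women.

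Which rule applies is for the sponsor to set. The mailed, video-verified test already used for remote consent and home testing shows that this need not add a visit. The cost is protocol wording and at most a few urine tests.
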